5.2 EFFICACY

Evaluable Disease Assessment

A subject's disease assessment on a particular date will be considered evaluable if an overall response of complete response (CR), partial response (PR), stable disease (SD), progressive disease (PD), CR/unconfirmed (CRu), or relapsed disease can be established by the central, independent, blinded radiologists' and oncologist's assessments per the 1999 IWG-HNL.

Overall Response Rate (ORR)

The overall response rate is defined as the percentage of subjects with a CR, CRu, or PR as defined by the 1999 IWG-NHL criteria (Cheson et al, 1999). All subjects that do not meet the criteria for response for a given analysis will be considered non-responders. The ORR will be calculated separately based on the central, independent, blinded radiologists' and oncologist's assessments and the investigator's assessment.

The primary endpoint is based on ORR by week 28. This is defined as the percentage of subjects who have achieved CR, CRu, or PR on or before week 28. To allow for a window around the scheduling of the week 28 visit, assessments done on or before week 30 (week 28 + 2 weeks) will be considered in this analysis.

For the secondary efficacy endpoint of RD of ORR at week 12, assessments done on or before week 14 (week 12 + 2 weeks) will be considered in the calculation of ORR.

Time-to-Event Endpoints

Time-to-event in days will be calculated as (event date – start date + 1). The duration in days may be converted to months as $12 * (\text{number of days} / 365.25)$ or to weeks as $\text{number of days} / 7$.

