8.5.6 Dose Adjustments, Dose Escalation and Stopping Rules

8.5.6.1 Dose Adjustments and Dose Escalations

There are no recommended dose adjustments or escalations for IP (ABP 798 or rituximab).

If any scheduled dose of IP in the first 4 visits (ie, visit 1, visit 2, visit 3, and visit 4) is delayed from the scheduled visit date (by more than 3 days), then the dose will be administered as soon as possible and subsequent doses will be adjusted accordingly to remain once per week from the adjusted dose date.

Regardless of previous dose delays, doses at visits 5 and 6 should be given according to the original schedule on weeks 12 and 20. If the scheduled dose for visits 5 and 6 is delayed by more than 15 calendar days from the scheduled visit date, then this will be considered a missed dose. The next dose should be given on the next scheduled visit date.

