8.6 Efficacy and Safety Variables

8.6.1 Efficacy and Safety Measurements Assessed

A schedule of assessments and procedures is presented in [Table 1](#).

Table 1. Schedule of Assessments and Procedures

	Screen ≤ 28 days	Treatment Phase							End of Study /Week 28 (± 7 days)
		Visit 1 Baseline Day 1, Week 1	Visit 2 Week 2 (± 3 days)	Visit 3 Week 3 (± 3 days)	Visit 4 Week 4 (± 3 days)	OPTIONAL Visit 4a Week 5 (± 3 days)	Visit 5 Week 12 (± 7 days)	Visit 6 Week 20 (± 7 days)	
General Assessments									
Informed consent form	X								
Post-infusion observation (4 hour)		X ^a							
Medical and medication history	X								
Physical examination	X	X ^b	X	X	X		X	X	X
Vital signs ^c	X	X ^d	X ^d	X	X		X	X	X
Electrocardiogram ^e	X								X
ECOG performance status	X								X
Clinical disease assessment		X	X	X	X		X	X	X
Concomitant medication	X	X	X	X	X		X	X	X ^f
Adverse event recording	X ^g	X	X	X	X		X	X	X
Treatments									
Dosing of ABP 798 / rituximab ^h		X	X	X	X		X	X	
Disease Assessments									
CT Scan	X ⁱ						X		X ^j
Bone marrow biopsy ^k	X								X ^k
Laboratory Assessments									
Serology (HBsAg, HBcAb, HCV)	X								
Serum chemistry ^{l,m}	X	X ^m	X	X	X		X	X	X
Hematology ^m	X	X ^m	X	X	X		X	X	X
Pregnancy ⁿ	X								
PK sampling ^{o,p,q}		X ^p	X	X	X ^p	X ^p	X	X	X
Pharmacodynamic (CD19+ cell count) ^{q,r}		X	X	X	X				X
Antidrug antibodies ^{q,s}		X					X	X	X
IgG and IgM ^q		X	X	X	X				X

CT = computed tomography; ECOG = Eastern Cooperative Oncology Group; HBcAb = hepatitis B core antibody; HBsAg = hepatitis B surface antigen; HCV = hepatitis C virus antibody; Ig = Immunoglobulin.
(See footnotes below)

- ^a The first 12 randomized subjects will be observed for safety for 4 hours after the first administration of IP.
- ^b Includes weight and height **within 8 days of visit 1**.
- ^c Systolic blood pressure and diastolic blood pressure will be measured on the same arm (preferentially on the left arm) after the subject has been in a supine/sitting position for 5 minutes.

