9.6 Week 28/End of Study

For subjects completing the treatment phase, the EOS visit will be at week 28, 8 weeks (± 7 days) after the last dose of IP. For subjects who do not complete the treatment phase, the EOS visit will be 8 weeks (± 7 days) after the last dose of IP. **Subjects who discontinue from the study due to disease progression should have a CT scan (as described below) prior to initiation of new anti-cancer treatment, if deemed clinically acceptable.**

At the EOS visit (**week 28 or 8 weeks after the last dose of IP**), the following assessments will be performed:

- physical examination, including evaluation of body systems
- vital signs (systolic and diastolic blood pressure, pulse, respiration rate, and temperature)
- standard 12-lead ECG
- ECOG performance status
- clinical disease assessment
- CT (not required if performed within the previous 4 weeks) of the neck (if palpable lymph node >1.0 cm or if performed at baseline), chest, abdomen, and pelvis.
- bone marrow biopsy (only required if bone marrow involvement is identified at baseline **for CR confirmation; if a confirmatory bone marrow assessment is not obtained, these subjects should be considered as only having a PR**). **The bone marrow biopsy can be performed at ± 14 days in relation to the study visit date.**
- clinical laboratory testing, including serum chemistry and hematology
- collection of samples for PK, antidrug antibodies, CD19+ cell count, and IgG and IgM levels

Any changes in concomitant medications since the last assessment will be recorded.

Any additional treatment for lymphoma will be recorded. All AEs, including increases in severity or frequency of pre-existing conditions, will be recorded in the eCRF through the week 28 visit. SAEs will be reported as outlined in [Section 11.2.2](#). Any SAEs ongoing at week 28 will be followed until they resolve or are considered chronic or stable.

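### Does the week-30 cut-off for the primary response endpoint miss end-of-study scans that the protocol permits?

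*SAP*

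**What the plan says.** SAP 5.2 counts a subject as a responder if CR, CRu or PR is reached on or before week 28. It then adds an allowance: "assessments done on or before week 30 (week 28 + 2 weeks) will be considered in this analysis". The reason it gives is "To allow for a window around the scheduling of the week 28 visit". Anyone without a counted response falls under the rule that "All subjects that do not meet the criteria for response for a given analysis will be considered non-responders". SAP 5.1 defines study day from the first dose but does not convert week 30 into one.

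The protocol describes the timing of the end-of-study (EOS) visit in two ways.

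- **Calendar.** The column heading in Table 1 (section 8.6.1) reads "End of Study /Week 28 (± 7 days", and section 8.3 also puts the visit at week 28.
- **Last dose.** Section 9.6 says that, for those who complete treatment, "the EOS visit will be at week 28, 8 weeks (± 7 days) after the last dose of IP". Later in the same section the visit is "week 28 or 8 weeks after the last dose of IP".

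On the week-20 dose (visit 6), section 8.5.6.1 says that "doses at visits 5 and 6 should be given according to the original schedule on weeks 12 and 20", whatever delays came before. If that dose is "delayed by more than 15 calendar days from the scheduled visit date, then this will be considered a missed dose". Table 1 and section 9.5 give visit 6 a window of ± 7 days. Table 1, footnote j, allows the EOS CT up to 28 days before the visit.

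**The concern.** The cut-off exists to absorb scheduling slack around the final scan. On the dose-anchored reading of 9.6, a late week-20 dose pushes that scan back, and the slack the protocol tolerates (15 days for the dose plus 7 for the visit) exceeds the 14 days the SAP allows. A subject whose first response shows on such a scan would be scored a non-responder on the primary endpoint. The investigator-assessed analysis on the full analysis set applies the same cut-off, so it would not reveal the loss. The per-protocol analysis would not either, unless the subject were excluded at blinded review.

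A second worry is that a limit given only in weeks leaves the programmer to choose a day. Visit numbering points to day 204, while dividing days by 7, as the SAP does for time-to-event endpoints, points to day 210.

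**Working it through.** **Convention.** Table 1, footnote r, equates week 2 with day 8, so week w starts on day 7(w − 1) + 1.

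- Week 20: 7 × 19 + 1 = day 134
- Week 28: 7 × 27 + 1 = day 190
- Week 30: 7 × 29 + 1 = day 204

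**The plan's own figure.** Week 28 + 2 weeks = 190 + 14 = day 204, which matches the start of week 30.

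**Latest EOS scan under each reading**

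| Case | Sum | Latest day | Against day 204 |
|---|---|---|---|
| Calendar anchor | 190 + 7 | 197 | 7 days inside |
| Dose anchor, visit 6 within ± 7 days | 134 + 7 + 56 + 7 | 204 | exactly covered |
| Dose anchor, visit 6 late by 15 days | 134 + 15 + 56 + 7 | 212 | 8 days past |
| Week-20 dose missed, week-12 dose (day 78) 15 days late | 78 + 15 + 56 + 7 | 156 | covered |

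The third row is the only one with a gap. It needs a dose 8 to 15 days late, which is outside the visit-6 window but not missed under 8.5.6.1. The combined lateness of dose and scan must also exceed 14 days.

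**Other readings of week 30.** Dividing days by 7, or counting to the last day of week 30, gives day 210. Thirty elapsed weeks gives day 211. Day 212 lies past these by 2 days and 1 day. The choice matters only for scans on days 205 to 211.

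**Share of EOS scans lost among subjects dosed 8 to 15 days late.** Assume delays spread evenly over 8 to 15 days and EOS visits spread evenly over the 15 days of the ± 7-day window.

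- CT on the visit day, cut-off 204: for delay d the share is (d − 7)/15. The mean over d = 8 to 15 is 4.5/15 = 30%.
- CT on the visit day, cut-off 210: (1 + 2)/(8 × 15) = 2.5%.
- CT spread evenly over the visit day and the 28 days before it, cut-off 204: there are 15 × 29 = 435 combinations per delay. The number lost is k(k + 1)/2 for k = 1 to 8, which sums to 120 with mean 15. 15/435 = 3.4%.

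**Lost responders per arm of 125.** The documents give none of the following inputs; all are assumed. Between 1% and 10% of subjects have the week-20 dose 8 to 15 days late, 30% to 50% of these have no earlier response, and 20% to 40% of those first respond at EOS.

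- Low: 125 × 0.01 × 0.3 × 0.2 = 0.075 first responders at EOS
- High: 125 × 0.10 × 0.5 × 0.4 = 2.5
- Times 30%: 0.02 to 0.75
- Times 3.4%: 0.003 to 0.09
- Times 2.5%: 0.002 to 0.06

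**Effect on the risk difference.** One unmatched subject is 1/125 = 0.8 percentage points. The highest figure, 0.75 lost responders, all in one arm and none in the other, is 0.75/125 = 0.6 points. The noninferiority margin is 15 points.

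**The case for a change.** The best argument for acting is that the dose anchor is a natural reading. Section 9.6 attaches the ± 7 days to the interval since the last dose, and other sections use the same interval for early discontinuation. No passage says which anchor governs after a late visit 6. SAP 1.1 was written to protocol version 3.0, the protocol is now at version 5.0, and the SAP itself announces a final version before database lock. A sentence there would cost almost nothing and would avoid a choice made after unblinding.

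Some of this stands. The day number is not printed, and 8.5.6.1, 9.6 and Table 1 leave EOS timing after a late week-20 dose unsettled. Those passages must be reconciled by the sponsor, and nothing here says which should prevail.

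Two parts do not stand. The allowance does not defeat its own purpose: it covers every visit kept within its window, on either anchor. Nor is the day really open. The SAP explains its limit as two weeks after week 28, and with week 2 equal to day 8 that is day 204. SAP section 10 also requires written specifications for the derived datasets and independent reprogramming with a full match, so a difference of interpretation should surface before results are produced.

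Moving the limit to day 212 would carry its own cost. A common fixed cut-off is a legitimate definition of response by week 28. Stretching it for everyone to catch a rare off-schedule scan changes the primary endpoint for little gain.

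**Conclusion.** No change to the plan follows. The date arithmetic behind the worry is right: day 212 is reachable on one reading of 9.6 and lies past every reading of week 30. But it needs a week-20 dose outside its visit window, a late EOS scan despite the freedom to scan up to 28 days early, and no counted response before that scan. For visits kept to schedule, the two-week allowance is sufficient on both anchors.

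The expected loss is under one responder per arm even at the top of the assumed range, and at most 0.09 with cut-off day 204 if CT dates are spread over the permitted 28 days. Randomization and the identical rule in both arms give no reason to expect the loss to favour either product, so no conclusion about equivalence would turn on it. The size rests on assumed rates of delay and late first response. The Independent Review Charter, which may set imaging windows, was not available. The missing study day is a programming detail that the SAP's own wording resolves to day 204.

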5.3 PHARMACODYNAMICS

Complete depletion of CD19+ cell count

Complete depletion of CD19+ cell count is defined as CD19 cell count $< 0.01 \times 10^9/\text{liter}$.

5.4 SAFETY

Event of Interest (EOI)

An EOI is defined as a noteworthy event for a particular product or class of products that a sponsor may wish to monitor carefully. It could be serious or non-serious, and could include events that might be potential precursors or prodromes for more serious medical conditions in susceptible individuals (Council for International Organizations of Medical Sciences (CIOMS) VI, 2005). The EOIs that will be monitored in this study are:

- infusion reactions
- tumor lysis syndrome
- cardiac disorders
- serious infections
- severe mucocutaneous reactions
- hematological toxicity
- progressive multifocal leukoencephalopathy
- GI perforation

AE preferred terms that are potentially representative of the EOI will be retrieved for review and analysis using the latest version of pre-specified Standardized MedDRA Queries (SMQs) if available.

Infusion reaction and tumor lysis syndrome EOIs will be summarized separately for:

- all events and
- events with onset day coincident with first IP infusion or the day after the first IP infusion.

If no SMQ is available for use as a search tool for a given EOI (e.g, infusion reactions) a customized search strategy will be developed and the preferred terms used in that search will be provided in an appendix to the SAP prior to the database lock.

Exposure-adjusted Incidence Rates of Adverse Events

Exposure-adjusted incidence rate is calculated as the number of subjects in a treatment group that experienced the event at least once divided by the total subject exposure times in the group. For subjects who experience the event, the exposure time is calculated as the time from the first dose date of IP to the onset of the first event. For subjects who do not experience the event, the exposure time is calculated as the time from the first dose of IP to the minimum of the end of study (EOS) visit date and death date.

Last Known Date Alive

The last known date alive will be the maximum of: end of study date, non-fatal AE start and stop dates, IP administration dates, serum chemistry and hematology sample collection dates, ADA sample collection dates, concomitant medication dates, vital sign dates, PK sample collection dates, and NHL lesion assessment dates.

Overall Survival (OS)

On-study OS is defined as the time from randomization to the date of death. Subjects who have not died before the week 28/EOS visit will be censored for OS at the last known date alive on or prior to EOS.

Progression-free Survival (PFS)

PFS is defined as the time from randomization until the first occurrence of disease progression per 1999 IWG-NHL criteria or death from any cause. For subjects alive and progression-free at the week 28/EOS visit, PFS will be censored at the date of the last disease evaluation demonstrating lack of progression. Subjects who have no post-baseline disease assessments will have their PFS times censored on the date of randomization. PFS will be calculated separately based on the central, independent, blinded radiologists' and oncologist's assessments and the investigator's assessment of progression.

Treatment-emergent Adverse Event

A treatment-emergent AE is defined as an AE that begins or increases in severity or frequency on or after the date of first IP and up to the EOS visit.

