- 14-6.1.17. Fatal Treatment-emergent Adverse Events by Preferred Term (Safety Analysis Set)
- 14-6.1.18. Treatment-emergent Serious Adverse Events by System Organ Class, Preferred Term, and Maximum CTCAE Grade (Safety Analysis Set)
- 14-6.1.19. Treatment-emergent Serious Adverse Events by Preferred Term (Safety Analysis Set)
- 14-6.1.20. Treatment-emergent Adverse Events of Interest by Maximum CTCAE Grade (Safety Analysis Set)
- 14-6.1.21. Treatment-emergent Adverse Events of Interest by Maximum CTCAE Grade – Japanese Subgroup (Safety Analysis Set)
- 14-6.1.22. Infusion Reaction Treatment-emergent Adverse Events by Preferred Term and Maximum CTCAE Grade (Safety Analysis Set)
- 14-6.1.23. Infusion Reaction Treatment-emergent Adverse Events by Preferred Term and Maximum CTCAE Grade for Events with Onset Day Coincident with First IP Infusion or the Day After the First IP Infusion (Safety Analysis Set)
- 14-6.1.24. Tumor Lysis Syndrome Treatment-emergent Adverse Events by Preferred Term and Maximum CTCAE Grade (Safety Analysis Set)
- 14-6.1.25. Tumor Lysis Syndrome Treatment-emergent Adverse Events by Preferred Term and Maximum CTCAE Grade for Events with Onset Day Coincident with First IP Infusion or the Day After the First IP Infusion (Safety Analysis Set)
- 14-6.1.26. Infusion Reaction Treatment-emergent Adverse Events by Preferred Term (Safety Analysis Set)
- 14-6.1.27. Infusion Reaction Treatment-emergent Adverse Events by Preferred Term for Events with Onset Day Coincident with First

- IP Infusion or the Day After the First IP Infusion (Safety Analysis Set)
- 14-6.1.28. Tumor Lysis Syndrome Treatment-emergent Adverse Events by Preferred Term (Safety Analysis Set)
 - 14-6.1.29. Tumor Lysis Syndrome Treatment-emergent Adverse Events by Preferred Term for Events with Onset Day Coincident with First IP Infusion or the Day After the First IP Infusion (Safety Analysis Set)
 - 14-6.1.30. Cardiac Disorders Treatment-emergent Adverse Events by Preferred Term (Safety Analysis Set)
 - 14-6.1.31. Serious Infections Treatment-emergent Adverse Events by Preferred Term (Safety Analysis Set)
 - 14-6.1.32. Severe Mucocutaneous Reactions Treatment-emergent Adverse Events by Preferred Term (Safety Analysis Set)
 - 14-6.1.33. Hematological Toxicity Treatment-emergent Adverse Events by Preferred Term (Safety Analysis Set)
 - 14-6.1.34. Progressive Multifocal Leukoencephalopathy Treatment-emergent Adverse Events by Preferred Term (Safety Analysis Set)

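### Infusion reactions have a time-linked summary for the first infusion only; reactions to infusions 2 to 6 appear only in tables with no stated onset link to an infusion

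*SAP*

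**What the plan says.** SAP 5.4 (Event of Interest) lists infusion reactions among eight events of interest. On identification it says that "AE preferred terms that are potentially representative of the EOI will be retrieved for review and analysis", using a Standardized MedDRA Query where one exists. Infusion reactions are its example of an event that may have no such query; in that case "a customized search strategy will be developed and the preferred terms used in that search will be provided in an appendix to the SAP" before database lock.

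Two summaries are planned: "Infusion reaction and tumor lysis syndrome EOIs will be summarized separately for" two groups of events. One takes all events. The other takes "events with onset day coincident with first IP infusion or the day after the first IP infusion". Both draw on treatment-emergent events, which SAP 5.4 defines as starting or worsening "on or after the date of first IP and up to the EOS visit".

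SAP 9.8.1 adds a breakdown by preferred term and maximum CTCAE grade, but no timing condition. In SAP Appendix 3, Tables 14-6.1.22 and 14-6.1.26 are the unrestricted versions (by grade and by term), and Tables 14-6.1.23 and 14-6.1.27 are the first-infusion versions. No listed table covers infusions 2 to 6 with a timing condition, and none is broken down by infusion number.

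**The concern.** The SAP's own rule of infusion day or next day accepts that timing helps to separate a reaction to an infusion from another event with the same coded term. The rule is then applied to one infusion of six. The protocol does not confine its interest to the first infusion: timed vital signs for hypersensitivity are also required at visit 2 (protocol 8.5.1), the infusion-reaction rules in protocol 8.5.6.2 are not limited to the first dose, and antidrug antibody samples are taken before the week 12 and week 20 doses (protocol Table 1). A reader who asks whether the arms differ at those later infusions has no prespecified table that answers the question.

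The unrestricted tables contain the later reactions, but mixed with whatever else matches. Several symptoms that protocol 8.5.6.2 gives for infusion-related reactions, such as rash, nausea and dyspnea, can also occur far from an infusion. Unrelated matches that are equally common in both arms raise both reported rates and narrow the gap between them. In a biosimilarity trial that is the unfavourable direction, because it makes the products look more alike.

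**Working it through.** The documents give no expected infusion-reaction rate, margin or power, so there is no planned figure to reproduce. Two checks apply.

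**1. How much follow-up each summary covers**

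- Six infusions, at weeks 1, 2, 3, 4, 12 and 20 (protocol 8.3).
- Protocol Table 1 equates week 2 with day 8, so week w starts on day 7(w-1)+1. The infusions fall on days 1, 8, 15, 22, 78 and 134, and week 28 is day 190, which is 56 days after the last dose.
- Infusion day plus next day, all six infusions: 6 × 2 = 12 days; 12/190 = 6.3%.
- First infusion only: 2 days; 2/190 = 1.1%.
- Unrestricted tables: all 190 days.

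Counting follow-up as 28 × 7 = 196 days gives 12/196 = 6.1%, so the result does not depend on the convention. Of the 12 infusion-linked days, 10 belong to infusions 2 to 6 and have no time-linked table. These are shares of time, not of events.

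**2. What unrelated matches do to the arm difference**

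Let p be the true proportion of subjects with an infusion reaction and b the proportion with at least one unrelated match, equal in both arms and independent of p. Then

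- reported proportion: p' = 1 - (1-p)(1-b)
- reported difference: p1' - p2' = (1-b)(p1 - p2)
- SE = √[p1'(1-p1')/125 + p2'(1-p2')/125], with 125 per arm from protocol 8.1

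Assumed for illustration: true rates of 20% and 30%, and b from 0 to 40%.

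| b | reported rates | difference (points) | SE (points) |
|---|---|---|---|
| 0% | 20% vs 30% | 10 | 5.4 |
| 10% | 28% vs 37% | 9 | 5.9 |
| 20% | 36% vs 44% | 8 | 6.2 |
| 30% | 44% vs 51% | 7 | 6.3 |
| 40% | 52% vs 58% | 6 | 6.3 |

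Example for b = 10%: 1 - 0.80 × 0.90 = 0.28 and 1 - 0.70 × 0.90 = 0.37; SE = √[(0.2016 + 0.2331)/125] = 0.059.

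The difference shrinks while its standard error grows. A second set of assumed rates shows the same pattern. For 30% versus 15%, the power of a two-sided 5% test, used only as a yardstick because no such test is planned, is 0.81 at b = 0 and 0.50 at b = 20%.

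**The case against.** The strongest reply is that the definition is not finished. Terms are retrieved for review as well as analysis, the customized search has not been written, a final SAP2 is to be issued before database lock (SAP section 1), and the table shells are a separate document that was not available here. A reader might infer that any matching event over 28 weeks will definitely count as an infusion reaction. The documents do not establish that: a narrow term list or a review rule could bring b close to zero. What stands is that no onset window beyond the first infusion is stated anywhere in the SAP, and that the only promised output of the search is its preferred terms.

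A reader might also infer that the 94% of follow-up outside the infusion windows can contribute only unrelated events. That is too strong, because a delayed reaction starting later than the next day falls there too. This is a good reason to keep the broad tables, and the SAP's remark that events of interest may include precursors of more serious conditions fits a deliberately wide capture. It does not explain why the narrow view stops at the first infusion.

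Finally, safety is summarized descriptively and inference is confined to the primary endpoint (protocol 12.6.4, SAP 9.5.3). No error rate or margin attaches to infusion reactions, and the SAP does not rank them above the other events of interest. That stands and limits the weight of the point.

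**Conclusion.** The concern holds in a limited form. As the SAP is written, reactions to five of the six infusions are tabulated only in summaries with no onset link to an infusion, and unrelated matches in those summaries would shrink any arm difference by the factor (1-b). With assumed rates of 20% and 30%, a 10-point difference would be reported as 10 points at b = 0 and 6 points at b = 40%. The direction follows from assuming that unrelated matches are equally common in both arms and independent of true reactions. The size depends on b and on the reaction rates, neither of which the documents give, and could be negligible. The reading that this threatens the trial's main conclusion is not supported: the equivalence assessment of response rate does not use these tables. The result is a gap in a descriptive safety comparison, worth closing because the remedy costs little.

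**What to change.** In SAP 5.4, SAP 9.8.1 and Appendix 3, add an infusion-reaction summary, by preferred term and maximum CTCAE grade, for listed terms with onset on the day of, or the day after, any infusion. Present it overall and by infusion number 1 to 6, with subjects who received that infusion as the denominator for each number.

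Apply the window to observed onset dates only, and report the number of matching events with a partial or missing onset date separately. This matters because SAP Table 2 often imputes the first-dose date for incomplete start dates, which would place such events in the window of infusion 1. SAP 5.5 describes imputed dates as serving treatment-emergence and concomitant-medication decisions, so the new rule would make explicit that they do not define this window.

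Keep Tables 14-6.1.22 and 14-6.1.26 as supportive, so that delayed reactions remain tabulated, and keep the first-infusion tables. Moving events outside the windows to a listing alone would go too far.

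The planned SAP2 and its search-term appendix are the natural place for the change. Adverse-event onset dates and dose dates are already recorded, so the cost is a date-window derivation and a few extra tables.
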